The prognostic value of circulating tumor cells (CTC) has been demonstrated in several studies in breast cancer, especially in advanced stage [35-38]. At UCSF in the laboratory of [name], we have demonstrated expertise in the measurement of CTC in patients with advanced stage breast cancer by IC/FC assay. CTC are first enriched with immunomagnetic beads coated with EpCAM, then EpCAM+, CD45-, nucleic acid+ cells are detected by flow cytometry. This technique is highly sensitive and reproducible, and allows sorting of cells for molecular analysis as well as analysis of cell surface markers[39]. In this trial, we will collect patient's peripheral blood samples every 4 weeks while on treatment and follow any reduction of CTC.

The mechanisms of hormonal resistance includes intrinsic and acquired pathways: decreased ER expression accounts for intrinsic resistance and the increased receptor tyrosine kinase pathway relates to acquired resistance [40-42]. We plan to analyze the mutation of PI3K/Akt and deletion of PTEN by sequencing in CTC (depending on numbers of cells, which in turn determines feasibility), in order to make a preliminary assessment of potential markers of response to pazopanib.

The tumor microenvironment plays an important role in cancer development and progression. Clinical studies have revealed that the increased T regulatory cells (Treg), high ratios of

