2.0 Objectives

2.1 Primary Objectives:

- To evaluate the clinical benefit rate (including complete response, partial response, and stable disease) at 12 weeks from the addition of pazopanib to a non-steroidal aromatase inhibitor (NSAI) (letrozole or anastrozole) in patients with hormone receptor positive advanced breast cancer progressing on the same NSAI hormone therapy.

2.2 Secondary Objectives:

- To evaluate progression free survival in patients treated with the combination of pazopanib and a NSAI.
- To evaluate safety of the combination of pazopanib and a NSAI.

2.3 Exploratory objectives:

- To quantify CTC as a surrogate marker of response.
- To evaluate specific markers including estrogen receptor, PI3K/AKT and PTEN on CTC at the time of study entry
- To evaluate the immune signature in serum samples from patients enrolled in this trial, including: IL-6, IL-8, VEGF, sVEGFR2, E-selectin, GRO-1, IL-4, IL-16, IP-10, IL-12, CSF-1, TIMP-1, OPN, HGF, SDF-1a and TRAIL.

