- ⁶ Blood urea nitrogen (BUN), Creatinine, Calcium, Potassium, Sodium, Glucose, Hematology: Hematocrit (HCT), Hemoglobin (HGB), Platelet count, White blood cell count (WBC), and differential are collected every 2 weeks until week 4, then every 4 weeks
- ⁷ Liver Function Tests (LFT) including Alanine aminotransferase (ALT), Aspartate aminotransferase (AST), Alkaline Phosphatase, Total Bilirubin and Albumin. Hematology: Hematocrit (HCT), Hemoglobin (HGB), Platelet count, White blood cell count (WBC), and differential. LFTs are collected every 2 weeks at weeks 3, 5, 7, and 9, then every 4 weeks and as clinically indicated.
- ⁸ UPC is required only if urine protein is $>$ 100.
- ⁹ CTCs will be collected at baseline, and then at 4 weeks, at 12 weeks and at the first visit documenting progression. One CellSave tube (7.5 ml) and one purple top tube (10 ml) should be sent at baseline, subsequent collections should include only one CellSave tube. Quantification of CTC will be conducted at [name] laboratory at UCSF
- ¹⁰ Serum will be collected at baseline and at 4 weeks. The cytokine levels will be measured by ELISA.
- ¹¹ Tissue biopsy is optional in this study, the safety of the biopsy will be determined by treating physicians.

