8.4 Follow-Up Assessments

The following assessments will be performed following completion of study treatment.

1. Physical examination including body weight.
2. Vital signs
3. Disease assessment (CT of chest, abdomen and pelvis for subjects with measurable disease; CT/MRI or Bone Scan for subjects with bone only disease, or PET/CT) PET/CT can be used in place if CT scan is diagnostic.
4. ECOG Performance Status.
5. 12-Lead EKG
6. Laboratory assessments including:
 - a. Clinical chemistry laboratory tests: Blood urea nitrogen (BUN), Creatinine, Calcium, Potassium, Sodium, Glucose, and Hematology: Hematocrit (HCT)
 - b. Hematology: Hematocrit (HCT), Hemoglobin (HGB), Platelet count, White blood cell count (WBC), and differential.
7. Blood for CTC at the first visit documenting disease progression if measurable ONLY. One CellSave tube (7.5 ml) will be drawn.
8. Record any AE(s) and SAEs and assign appropriate grade (NCI [CTCAE v4](#)).
9. Record all concomitant medications(s) added and/or changed.

Patients will be followed for four weeks after removal from study or until death, whichever occurs first. Patients removed from study for unacceptable adverse events will be followed until resolution or stabilization of the adverse event.

8.5 Correlative studies:

1. CTC quantification: peripheral blood will be collected for CTC at baseline, at 4 weeks and 12 weeks, then at the first visit documenting disease progression.
2. Evaluate PI3K/AKT and PTEN mutation on archival tissue sample and fresh tissue if available: PI3K/AKT and PTEN mutation will be tested on paraffin-embedded tumor tissue by DNA sequencing, this data will be compared to the mutation study obtain from CTC at the time of study entry and during the treatment.
3. Exploratory analysis of CTC will be undertaken depending on the number of CTCs for:
 - a. Estrogen receptor
 - b. PI3K/AKT and PTEN
 - c. Other genes based on availability of DNA and RNA and depending on the gene panel utilized for this trial
4. Changes in immune signature: serum will be collected within two weeks of study start and at 4 weeks. Immune signature (cytokines and chemokines) including: IL-4, IL-16, IP-10, IL-12, CSF-1, TIMP-1, OPN, HGF, SDF-1a and TRAIL will be measured by ELISA (Appendix IV)

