12.0 Statistical Considerations

The response rate with no additional treatment in women with disease progression while receiving aromatase inhibitors is expected to be <5%. We will consider an overall response rate of 20% to be clinically meaningful. For the purpose of this study, response will be defined as clinical benefit rate, including complete response, partial response, and stable disease for at least 12 weeks.

Therefore, we used the American Cancer Society's website (http://cryptnet.net/kepner/one_sample.html) for a 2 stage design with $p_0=0.05$, $p_1=0.20$ and power 80% at $\alpha=5\%$. This design specifies that if 0 of the first 14 eligible and evaluable subjects do not respond to the treatment at 12 weeks, then we are unlikely to reach a true overall response rate of 20%. The 15th patient will not be enrolled until we have confirmed that we have met criteria of at least 1 responses (response defined as clinical benefit) observed in the first 14 patients, to proceed to the second stage. An additional 13 patients will be enrolled in stage 2 for a total of 27 patients. If at least 4 of the total patients respond, we will conclude that the addition of pazopanib in this setting has the possibility of reversing resistance to hormone therapy with aromatase inhibitors. Using this design, we will have a less than 5% chance of incorrectly accepting the null hypothesis ($\alpha=0.05$), and an 80% chance of correctly rejecting the null hypothesis ($\beta=0.2$).

To determine whether the level of cytokines at baseline and during treatment could predict response to antiangiogenic therapy, we will divide patients into two groups; responder and non-responder group. The student t test will be used to analyze the differences of cytokine levels at baseline and at 4 weeks between these 2 groups.

CTC quantification data will be correlated with response and time to progression.

We will make preliminary observations regarding mutations or deletions in PIK3CA and PTEN in patients with measurable CTC, correlating changes with response and disease history, as well as presence or absence of these alterations in archival tumor tissue.

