12.1 Endpoint Definitions

Primary endpoint:

- The primary endpoint of this study is clinical benefit (including complete response, partial response, and stable disease) of at least 12 weeks.

Secondary endpoint:

- PFS: evaluate progression free survival in patients treated with the combination of pazopanib and a NSAI in this trial
- Safety : adverse events, SAEs

Exploratory endpoints:

- Evaluate the impact of the combination of pazopanib and a NSAI on circulating tumor cells
- Evaluate the change of immune profile with the combination of pazopanib and a NSAI

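### Section 12.0 plans no estimate of CTC change for the CTC endpoint in 12.1, and its one CTC-count analysis, a correlation with outcome, names no time point and no baseline term

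*Combined protocol and SAP*

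**What the plan says.** - **Endpoint (12.1, exploratory):** "Evaluate the impact of the combination of pazopanib and a NSAI on circulating tumor cells".
- **Objective (2.3, exploratory):** "To quantify CTC as a surrogate marker of response".
- **Analysis (12.0):** "CTC quantification data will be correlated with response and time to progression". This is the only sentence in section 12 that analyses CTC counts. The sentence after it concerns PIK3CA and PTEN alterations.
- **Sampling (8.0, schedule footnote 9):** "CTCs will be collected at baseline, and then at 4 weeks, at 12 weeks and at the first visit documenting progression". Section 8.5 gives the same times.
- **Background (1.3):** the trial will take "peripheral blood samples every 4 weeks while on treatment and follow any reduction of CTC". No statistic is attached. The 4-weekly sampling also differs from 8.0 and 8.5, and these sections should be reconciled.
- **Prognosis (1.3):** "The prognostic value of circulating tumor cells (CTC) has been demonstrated in several studies in breast cancer, especially in advanced stage".

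The cytokine plan is fuller. Section 1.3 promises a within-patient comparison of change, and 12.0 names baseline and week 4 as the time points and a t test between responders and non-responders.

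**The concern.** There are two separate gaps.

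1. **Endpoint and analysis do not match.** In a single-arm trial, the effect of treatment on CTC can only be approached through each patient's change from her own baseline. A correlation with outcome does not say whether counts fell, by how much, or how precisely that is known.
2. **The correlation is under-specified.** There are baseline, week-4, week-12 and progression samples and two outcomes, and the text does not say which count is used or how baseline enters. Section 1.3 itself describes CTC as prognostic. If a patient's week-4 count tracks her baseline count, an unadjusted week-4 correlation can appear even when the on-treatment change carries no information. Set against an objective worded in terms of surrogacy, such a result could be read as more than it is.

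At stake is the interpretation of an exploratory biomarker result. The go/no-go rule and the final efficacy conclusion use clinical benefit only.

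**Working it through.** **1. The plan's own figure.** No figure is stated for any CTC analysis. The two-stage design that fixes the sample size does reproduce. With 14 + 13 = 27 patients, continuing on at least 1 response and succeeding on at least 4, the sum over x1 ≥ 1 of P(X1 = x1) × P(X2 ≥ 4 − x1) is 0.042 at p = 0.05 and 0.807 at p = 0.20. The plan states below 5% and 80%. So 27 patients are available at most.

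**2. What each analysis estimates.**

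| Item | Quantity needed | Provided by 12.0? |
|---|---|---|
| 12.1 endpoint: effect on CTC | mean or median within-patient change, with precision | no |
| 2.3 objective: CTC as marker of response | association of on-treatment CTC with outcome beyond baseline | association only; time point and baseline handling not stated |

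The first row needs no assumption.

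**3. Why baseline matters: a case checkable by hand.** Assume standardised log counts, correlation ρ between baseline and week 4, correlation −g between baseline and an outcome score, and no effect of change. Take ρ = 0.7 and g = 0.5.

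- Raw week-4 correlation with outcome: −ρg = −0.7 × 0.5 = −0.35. The two-sided 5% critical value at n = 27 is 0.381. Simulation (20,000 trials) gives significance in 44%.
- Partial correlation given baseline: the numerator is −ρg − ρ(−g) = 0. Simulated rejection is 5.1%.
- Unadjusted change score: (1 − ρ)g / √(2 − 2ρ) = 0.15 / √0.6 = 0.19. Simulated rejection is 16.5%, so subtracting baseline is not enough.

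**4. The same question with 12-week benefit as outcome.** All inputs other than n are assumed. Baseline log count b ~ N(0,1); week 4 = ρb + noise; P(benefit) = base^(HR^b), with base 0.2 or 0.4, HR 1.5 or 2.0 per SD, ρ 0.5, 0.7 or 0.9; n = 27; 8,000 trials per setting. CTC change has no effect.

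| Analysis | Significant at two-sided 5% |
|---|---|
| Week-4 count, unadjusted (Spearman) | about 10-52% (32% at HR 2.0, ρ = 0.7) |
| Week-4 count with baseline in a linear model | about 5% in every setting |
| Change score, unadjusted | about 6-19% |

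**5. What adjustment costs.** Let the week-4 count alone drive benefit at HR 2.0 per SD. Unadjusted power is about 61%. With baseline in the model it is about 49%, 37% and 16% at ρ = 0.5, 0.7 and 0.9. At the 20% target rate there are only 27 × 0.20 = 5.4 expected responders.

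**6. Precision of the missing estimate.** For a paired mean change, the 95% half-width is t/√n in units of the SD of change.

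- 27 pairs: 2.056/√27 = 0.40 SD. Power is 80% for a mean change of 0.56 SD (noncentral t).
- 20 pairs: 2.093/√20 = 0.47 SD. Power is 80% for 0.66 SD.

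**The case against.** A reader might infer that the plan excludes the baseline count, or that the 12.1 endpoint is not measured at all. The documents support neither reading. The 12.0 sentence is silent on baseline. Under 8.0 and 8.5 the CTC quantification data include the baseline sample, so the sentence would permit correlating baseline counts, changes or adjusted values. CTC is measured at baseline, week 4 and week 12, and 1.3 states an intent to follow reductions. What is missing is a planned statistic.

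It can also be said that no criterion for declaring surrogacy is set and no decision depends on CTC. If only association is claimed, an unadjusted week-4 association is a true association and not a false positive. That stands. The 10-52% are errors only for the question of whether on-treatment CTC adds anything to baseline.

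The simulation inputs are assumptions. The documents give no CTC distribution, they warn that molecular work depends on cell numbers, and zero counts or missing later samples could make the normal model and the full 27 pairs optimistic. Adjustment also costs real power. These points stand too, and they favour showing both results.

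None of this supplies the missing estimate of change. The 1.3 sentence is background without a method.

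**Conclusion.** The point holds as a minor one. Section 12.0 specifies no summary of CTC change for the 12.1 endpoint, and this follows from the text alone. Its correlation with outcome names no time point and no baseline handling, which leaves room for baseline prognosis to look like a marker of response. The size of that second problem is illustrative only: about 10-52% significant unadjusted against about 5% adjusted at n = 27, under an assumed HR of 1.5-2.0 per SD, an assumed baseline/week-4 correlation of 0.5-0.9, normal log counts, complete samples and no effect of CTC change. These percentages should not be read as this trial's error rate.

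Even with baseline in the model, a single arm can show association only. It cannot establish surrogacy or separate a treatment effect from change over time.

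**What to change.** In section 12.0, replace the CTC sentence with two items.

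1. **For the 12.1 endpoint:** report within-patient change in log(CTC+1) from baseline to week 4, with a 95% confidence interval and a signed-rank test. State the number of pairs and the number of zero counts. Report week 12 descriptively, since that sample falls at the same visit as the disease assessment for the primary endpoint.
2. **For the 2.3 objective:** report week-4 log CTC against 12-week clinical benefit and against PFS, with PFS counted from week 4 among patients still progression-free. Give each result both unadjusted and with baseline log CTC in the model. Interpret both as exploratory association and not as surrogacy.

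**Cost:** a few sentences and a little more analysis. The week-4 and week-12 blood draws are already scheduled. The adjusted model loses power when baseline and week-4 counts are highly correlated and responders are few, which is why both results are shown. Sample size, decision rule and primary analysis do not change.

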12.1 Endpoint Definitions

Primary endpoint:

- The primary endpoint of this study is clinical benefit (including complete response, partial response, and stable disease) of at least 12 weeks.

Secondary endpoint:

- PFS: evaluate progression free survival in patients treated with the combination of pazopanib and a NSAI in this trial
- Safety : adverse events, SAEs

Exploratory endpoints:

- Evaluate the impact of the combination of pazopanib and a NSAI on circulating tumor cells
- Evaluate the change of immune profile with the combination of pazopanib and a NSAI

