The most common adverse reactions (greater than or equal to 20%) were diarrhea, hypertension, hair color changes, nausea, anorexia, and vomiting. Grade 3/4 adverse reactions that differed by greater than or equal to 2% between arms were abnormal hepatic function, diarrhea, hypertension, and proteinuria. QT prolongation has been seen with pazopanib. Laboratory abnormalities occurring in >10% of patients and more commonly (>5%) in the pazopanib arm included increased transaminases, hyperglycemia, leukopenia, hyperbilirubinemia, neutropenia, hypophosphatemia, thrombocytopenia, lymphocytopenia, hyponatremia, hypomagnesemia, and hypoglycemia. Deaths due to serious adverse events include cerebrovascular accident, gastric cancer, gastrointestinal hemorrhage, hemoptysis, bowel perforation, cardiac failure, myocardial infarction, hepatic failure and pneumonia occurred more commonly in the pazopanib arm. Hepatic dysfunction is included as a boxed warning in the product label and two deaths were associated with hepatic failure.

Recently, a phase II trial was designed for patients with metastatic breast cancer, who failed 2-3 prior chemotherapy. Total 20 patients were recruited in this study, 70% were ER+, and all were Her-2/neu negative. Pazopanib monotherapy was given at 800 mg daily. One patient (5%) had a partial response, 11 (55%) had stable disease (SD) [four (20%) with SD > or = 6 months], and seven (35%) had progressive disease as their best response. One (5%) was not evaluable. The median time to progression was 5.3 months. Pazopanib did not cause significant severe toxicity aside from grade 3-4 transaminitis, hypertension, and neutropenia in three patients each (14% each) and grade 3 gastrointestinal hemorrhage in one patient (5%)[18].

Standard therapy for hormone receptor positive metastatic disease.

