The addition of antiangiogenic therapy to hormonal therapy has been investigated in several clinical trials. In a phase II single arm study, 27 patients with metastatic breast cancer who progressed on endocrine therapy alone were recruited. Patients were continued on the same hormone therapy to which they had become refractory with the addition of bevacizumab. Stable disease was seen in 18 patients (66%) [32]. In a multi-center feasibility trial performed at MSKCC and UCSF, 43 patients with treatment naïve metastatic ER positive breast cancer, stable or responding to NSAI treatment were treated with the combination of letrozole and bevacizumab. 74% of the patients had clinical benefit with a favorable PFS of 17.1 months compared with a 9-month historical PFS in postmenopausal women with MBC treated with letrozole alone in the first-line setting [33]. This study led to an ongoing Phase III trial with the U.S. cooperative group CALGB testing this combined therapy.

These data suggest that co-targeting the tumor with endocrine therapy as well as its associated vasculature using anti-angiogenic agents could lead to additive effects, resulting in more effective anticancer therapy, and potentially reversing acquired resistance to hormone therapy [34].

In this trial, we propose to evaluate the role of VEGFR blockade with the tyrosine kinase inhibitor pazopanib in combination with nonsteroidal aromatase inhibitors (NSAI) in patients who are progressing or have relapsed on the same NSAI hormone therapy given for advanced or early stage breast cancer. If this trial demonstrates clinical benefit, this all oral combination could be tested in both the neoadjuvant and metastatic settings in a randomized phase II design.

In order to investigate potential factors predicting response or resistance to pazopanib and NSAIs, several translational studies have been incorporated into this trial.

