8.3.6 Every 16 weeks (after week 12)

1. Disease assessment (CT of chest, abdomen and pelvis for subjects with measurable disease [unless indicated sooner by clinical findings] or Bone Scan for subjects with bone only disease, or PET/CT). PET/CT can be used in place if CT scan is diagnostic.
2. 12-Lead EKG

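### Does PFS, left without dating, censoring and estimation rules on a 16-week scan schedule, call for a change to the plan?

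*Combined protocol and SAP*

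**What the plan says.** Section 12.1 of the combined protocol and SAP lists PFS as a secondary endpoint in these words only: "PFS: evaluate progression free survival in patients treated with the combination of pazopanib and a NSAI in this trial". Section 12.0 gives methods for the primary two-stage rule, the cytokine comparison and the exploratory correlations, but none for PFS. It also uses a second time-to-event quantity without defining it: "CTC quantification data will be correlated with response and time to progression".

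The first on-treatment disease assessment is at week 12 (8.3.5) and later ones are every 16 weeks (8.3.6), "unless indicated sooner by clinical findings". Section 8.0 allows 7 days either side. Section 9.1 defines progression and includes a route without a scan: a patient who does not come back because the disease is worsening. It does not say how to date it.

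Two times are stated, neither tied to PFS: an analysis 12 weeks after the last enrolment (12.5) and follow-up of 6-8 months after it (12.3). Patients who leave the study are followed for four weeks (8.4).

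**The concern.** A progression found at a scheduled scan happened somewhere in the preceding 12 or 16 weeks. If it is dated at the scan, the Kaplan-Meier curve falls only at a few fixed times, and the median lands on one of them, usually above the truth. If all progressions are found this way, true medians of 4.0 and 5.3 months would both typically be reported as 6.4 months.

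The background in section 1.3 reads a single-arm PFS in just the way such a figure would distort: "a favorable PFS of 17.1 months compared with a 9-month historical PFS in postmenopausal women". With no rule written down, event dates, censoring and the data cut could also be chosen after the data are seen. At stake would be an over-favourable PFS figure for the combination.

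**Working it through.** **Inputs from the documents.** Scans at week 12 (8.3.5), then every 16 weeks (8.3.6), read as weeks 28, 44 and 60; window of 7 days (8.0); 27 evaluable patients (12.0); 18-month accrual (12.3); cuts at 12 weeks (12.5) and at about 26 and 35 weeks (the 6 and 8 months in 12.3).

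**Assumptions.** Exponential progression times, with true medians of 4.0, 5.3 and 9 months. The last two are borrowed from other trials in the background: "The median time to progression was 5.3 months" in 1.2, and the 9-month historical figure in 1.3. The share of progressions found at scheduled scans is not in the documents, so it is varied from 100% to 25%.

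**1. The plan's own figure.** None is given for PFS. The stated 80% power with alpha below 5% is for the primary rule: continue unless 0 of 14 respond, succeed with at least 4 of 27. The formula is P(≥4 of 27) − P(0 of 14) × P(≥4 of 13).
- At a 20% rate: 0.818 − 0.044 × 0.253 = 0.807.
- At a 5% rate: 0.0437 − 0.0015 = 0.042.

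Both reproduce, and neither uses a PFS date.

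**2. The scan grid.** At 4.348 weeks per month, weeks 12, 28, 44 and 60 are 2.76, 6.44, 10.12 and 13.80 months. The first step is 2.76 months and later steps are 16/4.348 = 3.68 months.

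**3. Population median if every event is scan-dated.** With S(t) = 2^(−t/m), the reading is the first scan at which S ≤ 0.5.
- m = 4.0: S(2.76) = 0.62 and S(6.44) = 0.33, so it reads 6.44 (excess 2.4).
- m = 5.3: 0.70 and 0.43, so it reads 6.44 (excess 1.1).
- m = 9: S(6.44) = 0.61 and S(10.12) = 0.46, so it reads 10.12 (excess 1.1).

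**4. Average shift with 27 patients.** Simulated mean Kaplan-Meier median minus the mean with exact dates, in months:

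| Found at scheduled scans | True 4.0 | True 5.3 | True 9 |
|---|---|---|---|
| 100% | 6.16 − 4.10 = 2.06 | 7.31 − 5.45 = 1.86 | 11.08 − 9.22 = 1.86 |
| 75% | 5.72 − 4.10 = 1.62 | 6.90 − 5.45 = 1.45 | 10.67 − 9.25 = 1.42 |
| 50% | 5.15 − 4.09 = 1.06 | 6.48 − 5.41 = 1.07 | 10.21 − 9.24 = 0.97 |
| 25% | 4.53 − 4.06 = 0.47 | 5.98 − 5.45 = 0.53 | 9.78 − 9.28 = 0.50 |

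The 7-day window barely moves the top row (6.20, 7.33 and 11.03).

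**5. Sampling error.** With continuous observation, the 10th-90th percentile range of the median is 2.7-5.7 months for a true 4.0 (width 3.0) and 3.7-7.6 for a true 5.3 (width 3.9).

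**6. Data cut.** All events scan-dated, cuts 12, 26 and 35 weeks after last entry; means are over trials that reach the median.
- True 4.0: 6.23, 6.17, 6.17.
- True 5.3: 7.35, 7.25, 7.37.
- True 9: 10.81, 11.26, 11.34, with the median not reached in 5.7%, 1.3% and 0.2% of trials.

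A 12-week cut gives up three to four events against a 29-week cut: 20.1 against 23.5 for a true 4.0, and 17.9 against 21.5 for a true 5.3. A 12-week pause between stages ("The 15th patient will not be enrolled until we have confirmed") changes little: 19.8 against 23.3, and 17.6 against 21.4.

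**The case for a change.** The best case for a change is that the open choices are real and closing them is cheap. A patient who deteriorates and does not return has no scan date. One who stops for toxicity is followed for only four weeks, and nothing says when that patient is censored. When all progressions are scan-dated, the reported median exceeds the truth in about 90% of simulated trials for a true 4.0 and 98% for a true 5.3. Progression-free proportions at week 28 would avoid the dating problem: with every progression scan-found and a 29-week cut they average 0.327 against 0.328 true, and 0.431 against 0.431.

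The omission and the direction of the bias stand. The simulation also leaves out stopping without progression, so the effect of that censoring has not been sized. The rest carries less weight.

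- The share of trials above the truth does not show how far above. A true median of 6.0 months gives 99% above for a typical excess of only 0.44 months.
- The comparison of 17.1 with 9 months concerns letrozole plus bevacizumab. No historical PFS comparison is planned here, and scan dating distorts one only so far as scan schedules differ. The next step is tied to the primary outcome: "If this trial demonstrates clinical benefit, this all oral combination could be tested".
- Writing down the conventional rule (Kaplan-Meier, progression dated when documented) would give the same median as the default. It would not remove the grid.
- Week-28 proportions and interval-censored fits are reasonable supporting summaries, but they are preferences. At 27 patients the proportion is imprecise too: the exact 95% interval for 9/27 is 17-54%.

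**Conclusion.** This is a specification gap that analysts can be expected to fill sensibly, and no change to the plan follows. The conventional reading is Kaplan-Meier, progression per section 9.1 or death as the event, detection dates, censoring at the last progression-free assessment, and the data available at the end of the 6-8 months of follow-up. The choice of cut moves the mean median by about 0.1 months for true medians of 4.0 and 5.3, and by about 0.5 months for 9.

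The upward reading is about 2 months on average at worst and about 0.5 months when a quarter of progressions are found at scheduled scans. It attaches to a descriptive endpoint with no target or test, whose sampling range is 3 to 4 months wide. The primary design reproduces (power 0.807, alpha 0.042) and is untouched.

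These sizes rest on exponential times, assumed true medians of 4.0 to 9 months, an assumed range for the scan-found share, and no stopping without progression. Whoever reads the eventual median should keep the 12- and 16-week scan intervals in mind.
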